Clinical Research Protocol

Protocol Title: Evaluation of the Lutronic PicoPlus for the treatment of dermatological conditions such as unwanted tattoos and benign pigmented lesions

Protocol Number: L16004

Version: 5.0

Date: May 23, 2019

Sponsor: Lutronic Global
[name]
[name]
Contact: [name], MBA
[contact]

Principal Investigators
[name]
[name], MBA
[name]
[name]
[name]
[name], PhD
[name]
[name]
[name]
[name], DO
[name]

Table of Contents

Table of Contents

1	Objective	3
2	Non-Significant Risk Determination.....	3
3	Study Device	3
3.1	Device Description	3
3.2	Background	5
4	Study Population	6
4.1	Inclusion Criteria.....	6
4.2	Exclusion Criteria	6
5	Study Design	7
5.1	Number of Subjects.....	7
5.2	Study Design.....	7
5.2.1	Group A Treatment Plan	8
5.2.2	Group B Treatment Plan	8
5.3	Investigational Sites	9
5.4	Study Duration.....	10
6	Study Treatment	10
6.1	Pre-Treatment	10
6.2	Anesthesia.....	10
6.3	Analgesic and anxiolytic oral medications.....	11
6.4	Biopsies.....	11
6.5	Study Treatment.....	11
6.6	Post-Treatment.....	12
6.7	Follow-Up Visits.....	12
7	Institutional Review Board Review	12
8	Informed Consent	13
9	Study Outcomes.....	13
10	Risks and Benefits	13
10.1	Potential Risks	13
10.2	Potential Benefits	14
11	Adverse Events	14
12	Subject Accountability.....	16
13	Records and Reporting	16
14	Confidentiality	16
15	Subject Payment	16
16	References.....	16
17	Appendix A. Patient Satisfaction Questionnaire.....	18
18	Appendix B: Clinician Grading Scales	19
18.1	Investigator's Global Assessment of Improvement.....	19
18.2	Subject's Global Assessment of Improvement.....	19
18.3	Subject Satisfaction Assessment.....	19
18.4	Blinded Reviewer's Global Assessment of Improvement	19
18.5	Melasma Area Severity Index (MASI).....	20

1 Objective

The objective of this investigation is to evaluate the Lutronic PicoPlus for the treatment of dermatological conditions, such as, but not limited to, unwanted tattoos and benign pigmented lesions. The primary objective is to evaluate the capability of the technology to remove unwanted tattoos and benign pigmented lesion including melasma. In this pilot protocol, the PicoPlus treatment may be compared to other commercially available medical laser devices as part of this study.

2 Non-Significant Risk Determination

In accordance with the definition of "Significant Risk Device" provided in 21 CFR 812.3, each device to be used in this study has been determined to be Non-Significant Risk devices based on the following:

- a) It is not an implant
- b) It is not purported or represented to be for use in supporting or sustaining human life and do not present a potential for serious risk to the health, safety or welfare of a subject
- c) It is not for a use of substantial importance in diagnosing, curing, mitigating, or treating disease or otherwise preventing impairment of human health
- d) Use of the device poses no risk to the health, safety, or welfare of a subject

3 Study Device

3.1 Device Description

The Lutronic PicoPlus System (Lutronic Corp, Seoul, S. Korea) to be used in this pilot study is an investigational device intended to be used for dermatological conditions including unwanted tattoos and benign pigmented lesions. All PicoPlus devices to be used in the study will bear the following required labeling:

**"CAUTION: Investigational Device.
Limited by Federal (or United States)
Law to Investigational Use."**

The PicoPlus System is a state-of-the-art Q-switched laser system with multiple handpieces and similar to the Cutera Enlighten laser system (Cutera Inc, Brisbane, CA) which received 510(k) market clearance (K160488, K140727 & K133945) from the Food and Drug Administration (FDA) on Oct. 28, 2016, Nov 6, 2014 and Aug 11, 2014, respectively. The Cutera Enlighten laser system is intended for use in surgical and aesthetic applications in the medical specialties of dermatology and general and plastic surgery.

The 1064 nm wavelength of the enlighten laser system is indicated for:

- treatment of benign pigmented lesions on patients with all skin types (Fitzpatrick I-VI)
- tattoo removal for dark colored tattoo inks and for multicolored tattoos containing dark colored tattoo inks on patients with all skin types (Fitzpatrick I-VI)

The 532 nm wavelength of the enlighten III laser system is indicated for:

- treatment of benign pigmented lesions on patients with Fitzpatrick skin types I-III
- tattoo removal for lighter colored tattoo inks, including red and yellow inks, on patients with Fitzpatrick skin types I-III

The 670 nm wavelength of the enlighten III laser system is indicated for treatment of benign pigmented lesions on patients with Fitzpatrick skin types I-III.

Table 1 provides a summary of PicoPlus system specifications and comparison to the Cutera Enlighten device.

Lutronic's new PicoPlus system delivers picosecond and nanosecond pulse durations at 1064nm and 532nm wavelengths plus 2 wavelengths from solid dye handpiece, the 595nm and 660nm. The touch screen control of the PicoPlus device auto detects the user selected handpiece (5 choices: 1064/532 with Zoom & Pico Toning Collimated, 595nm, 660nm and 1064nm Focused Dots) attached to the articulated arm (Figure 1). The Zoom and Pico Toning Collimated handpieces allow the user to select a range of spot sizes and the touch screen's available parameters automatically adjusts to the selected spot size. A detailed description of the system and its capabilities is provided by Lee et al., (1)

Table 1. PicoPlus™ Specifications

	Lutronic PicoPlus	Predate Cutera Enlighten
Type	Q-switched Nd:YAG laser	Q-switched Nd:YAG laser
Wavelength	532nm, 595nm, 660nm and 1064nm	532nm, 670nm and 1064nm
Maximum Delivered Energy	300mJ at 532nm 800mJ at 1064nm 110mJ at 595nm 90mJ at 660nm	300mJ at 532nm 600mJ at 1064nm 125mJ at 670nm
Maximum Fluence	1064nm: 100 J/cm ² @ 1mm, to 1 J/cm ² @ 10mm 532nm: 45J/cm [contact] to 0.45 @9mm	2.5 J/cm ² at 532nm 10 J/cm ² at 1064nm
Pulse Duration	550 ps, 2 ns	532&1064nm 750 ps or 2 ns; 660ps 670nm
Repetition Rate	1, 2, 5 or 10 Hz or single shot	1, 2, 3.3, 5 or 10 Hz or single shot
Handpiece Spot Size	(1) Zoom 1- 6 mm @ 1064 nm 0.9 - 5.3 mm @ 532 nm (2) Pico Toning Collimated 6 - 10mm @1064nm 4.3 - 9mm @ 532nm (3) 2, 5mm @ 595nm (4) 2, 3mm @ 660nm (5) Focused Dots 7.4x7.4mm @1064nm with 81 focused spots of 100um each	2, 3, 4, 5, 6, 7 or 8 mm 532 and 1064nm (2, 3, 4, 5 & 6mm 670nm)
User Interface	LCD color touchscreen	Push-button control or LCD color touchscreen
Delivery System	Articulated arm with laser handpiece	Articulated arm with laser handpiece
System Cooling	Air plus water cooling	Closed cycle water to air heat exchanger
Aiming Beam	Laser diode 655nm <5mW	Laser diode 635nm <1mW
Weight	142 kg	324lbs (147kg)
Dimension	483x1078x1119mm 19x45x30 in	910x510x840mm 36 X 20 X 33 in
Power	100-240VAC max 15A, 50-60Hz	100-120VA, 20A 240VAC 15A, 50-60Hz

Figure 1. Lutronic PicoPlus System and accessories

FEATURES

LUTRONIC

3.2 Background

The nanosecond domain Q-switched Nd:YAG laser (for example Lutronic's Spectra), operates under the theory of selective photothermolysis at the wavelengths of 532 nm and 1064 nm, and has become the treatment of choice for removal of tattoos and pigmented lesions. The Spectra offers highly selective pigment removal with minimal thermal damage to the adjacent tissues. The nanosecond QS lasers are safe and effective in the treatment of tattoos, although treatment sessions are often painful and as many as 6 to 10 treatments are necessary to achieve acceptable clearance. Also the ns-based approach has some limitations due to the mostly thermal nature of the reaction, and in tattoo removal, the increasing variety of colors used often results in incomplete removal of the tattoo. Moving into the picosecond domain removes much of the photothermal nature of the reaction, replacing it with a nonlinear photoacoustic effect. The more complete breakup and smaller resulting particles are more readily removed by natural healing mechanisms through lymphatics, phagocytosis or trans-epidermal elimination. The photoacoustic effect also transfers most of the energy to mechanical forces resulting in a significantly reduced thermal effect on surrounding tissue compared to ns-domain. The lessened thermal effect is thought to account for the reduction in tissue side effects observed using picosecond laser treatment.

Since the introduction of the Picoseure 755nm picosecond laser (Cynosure), several other picosecond laser devices have been launched that now include 1064nm, 532nm, 785nm and 670nm wavelengths. Numerous published studies demonstrate the ability of

picosecond lasers (2-15) to achieve better tattoo clearance in fewer treatments with less tissue side effects and similarly remove unwanted pigmented lesions.

For pigmented lesions the target chromophore is the melanin granules located inside the melanosomes generated by melanocytes. Using pulses significantly less than the thermal relaxation time of melanosomes and melanin granules, *i.e.* in the ps domain, should get even better results than the ns-domain, and by photooptical breakdown should induce a nonlinear reaction in the target so that destruction would not be thermal, but mechanical in nature [15].

The purpose of this exploratory investigational study is to evaluate the enhanced capabilities of the Lutronic PicoPlus laser system with its 5 handpieces and the broader range of power output for removal of unwanted tattoos or pigmented lesions as well as to explore other treatment opportunities.

4 Study Population

Adults between 18 and 60 years of age with unwanted tattoos or suitable dermatological condition who provide informed consent, and who meet inclusion/exclusion criteria.

4.1 Inclusion Criteria

- Male or Female
- Adults between age 18 and 60 years old
- Group A: Fitzpatrick skin type I – VI for unwanted tattoos and Group B: Fitzpatrick Skin Types I – IV for benign pigmented lesions and other conditions
- Unwanted tattoo that contains single or multi-color ink, and
 - Willing to cover tattoos with a bandage or clothing; and/or have very limited sun exposure and use an approved sunscreen of SPF 50 or higher on the treated area starting 2 to 4 weeks before the treatment
- Ability to read, understand, and sign the Informed Consent Form
- Willing to have digital photographs taken of the treatment area and agree to use of photographs for presentation, educational or marketing purposes.
- Understands and accepts the obligation not to undergo any other procedures in the areas to be treated
- Willing and able to comply with all study participation requirements including returning for follow-up visits and abstaining from exclusionary procedures for the duration of the study

4.2 Exclusion Criteria

- If receiving treatment for unwanted tattoo: double tattoos (tattoo over tattoo), history of allergic reactions to pigments following tattooing, local anesthetics or topical antibiotics
- If receiving treatment for benign pigmented lesions including melasma: history of use of a lightening medication (hydroquinone, tranexamic acid), isotretinoid (or retinoid), or light-sensitive medication in the last 6 months

- Known cardiovascular disease or cardiac surgery that in the opinion of the investigator would interfere with study treatments
- Previous interventions or treatment with another device in the target area within 6 months of enrollment or during the study
- Pregnant or lactating or planning pregnancy before end of study
- Presence of an active systemic, local skin disease, medication or condition that may affect wound healing or interfere with participation or treatment to the active area.
 - Active or recurrent cancer of current chemotherapy or radiation therapy
 - History of seizure disorders due to light
 - History of vitiligo, eczema, or psoriasis
 - History of connective tissue disease, such as systemic lupus erythematosus or scleroderma
 - History of pigmentary disorders, particularly tendency for hyper- or hypo-pigmentation
 - History of disease stimulated by heat, such as recurrent herpes simplex and/or herpes zoster (shingles) in the treatment area, unless treatment is conducted following a prophylactic regimen
 - History of keloid scarring, hypertrophic scarring or of abnormal wound healing.
 - History of immunosuppression/immune deficiency disorders or currently using immunosuppressive medications.
 - History of seizure disorders due to light.
 - Suffering from coagulation disorders or taking prescription anticoagulation medications
 - History of keloid scarring, hypertrophic scarring or of abnormal wound healing Any use of medication that is known to increase sensitivity to light according to Investigator's discretion
- Excessive or recent significant tan in areas to be treated or unable/unlikely to refrain from tanning during the study
- Current smoker or history of smoking within 3 months of study participation
- Systemic use of corticosteroid or isotretinoin within 6 months of study participation
- Anytime in life, having have used gold therapy (gold salts) for disorders such as rheumatologic disease or lupus
- Any physical or mental condition including alcohol or drug abuse that in the opinion of the investigator could interfere with subject's suitability for inclusion in study

5 Study Design

5.1 Number of Subjects

Up to 100 subjects will be enrolled in this study. Subjects will be enrolled only after written approval to conduct this study has been received from an Institutional Review Board (IRB); and only after providing signed, informed consent to participate in the study.

5.2 Study Design

The study design is a multicenter exploratory, open-label, clinical trial comparing each subject's condition before to after treatment. Subjects will be selected and assigned to Group A for treatment of unwanted tattoos and Group B for treatment of unwanted benign pigmented lesions, melasma or other skin conditions such as skin rejuvenation.

5.2.1 Group A Treatment Plan

Subjects receiving treatment for unwanted tattoos (Group A) will receive 1 - 8 treatments (typically 3 – 5) at 2 - 12 week intervals (typically 6- 8 week) with an optional follow-up visit 1-2 weeks after the first treatment for safety evaluation and a final follow-up 1-3 months after the last treatment for safety and efficacy evaluation. At the discretion of the Investigators, additional follow-up visits may take place to observe the time course of reactions after treatment and/or to assess efficacy (i.e. 6 month follow-up). Table 2 summarizes the visit schedule and Table 3 summarizes the study event schedule. The screening/pre-treatment visit and first treatment visit may occur on same day.

5.2.2 Group B Treatment Plan

Subjects receiving treatment for unwanted benign pigmented lesions or other dermatological condition such as skin rejuvenation (Group B) will receive 1 - 8 treatments (typically 2 – 4) at 1 – 12 week intervals. For facial treatments the typical interval is 3 – 5 weeks and for off-face the interval is typically a little longer. Subjects may have an optional follow-up visit 1-2 weeks after the first treatment for safety evaluation and at least one final follow-up visit 1-3 months after the last treatment for safety and efficacy evaluation. At the discretion of the Investigators, additional follow-up visits may take place to observe the time course of reactions after treatment and/or to assess efficacy. Table 2 summarizes the visit schedule and Table 3 summarizes the study event schedule. The screening/pre-treatment visit and first treatment visit may occur on same day.

Table 2. Study Visit Schedule

Visit	Group A Tattoo	Group B Pigment and other conditions
Evaluation	1	1
Treatment	1 to 8 treatments Typically 3-5	1 to 8 treatments Typically 2-4
	Typically at 6 -8 week interval, but PI could schedule at 2 to 12 weeks interval	Typically at 3 - 5 week interval, but PI could schedule at 1 to 12 weeks interval
Follow-up	1 at least 3 months after last treatment 2 nd follow-up 6mo	1 - 3 months after last treatment

Table 3. Study Event Schedule

Procedures	Site Initiation	Screen / PreTx Evaluation	1st Tx Visit	Optional 1 – 2 wk safety evaluation	2nd Tx Visit	3rd Tx Visit, etc.	1 - 3 month follow-up visits (s)
Review protocol & study requirements	x						

Inclusion / Exclusion		x					
Med History Review		x	x	x	x	x	x
ICF		x					
Pre-Treatment Skin Evaluation		x	x	x	x	x	x
Laser Treatment			x		x	x	
Immediate Post-Tx Skin Evaluation			x		x	x	
Pre-Tx Clinical Photos			x	x	x	x	x
Post-tx Photos			x	x	x	x	
Patient Satisfaction Questionnaire							x

5.4 Study Duration

This study is not expected to exceed 36 months in duration.

6 Study Treatment

6.1 Pre-Treatment

Prior to the first treatment, the Investigator or his/her designee will obtain a medical history for each subject and determine study eligibility in accordance with the Inclusion and Exclusion Criteria specific to this protocol. Subjects will be directed to not use self-tanners within the target treatment area for at least 4 weeks prior to treatment and to avoid using harsh skin treatments such as depilatories, abrasive cleansers, etc. for 1-2 weeks prior to treatment. If the patient is a female capable of pregnancy, a urinary pregnancy test will be performed prior to study participation to determine if she is pregnant. If the result of the test is positive or if the female is breast feeding, she is not eligible to participate in study. The treatment area can be on the face, chest arms, legs or body. High-resolution digital photographs will be taken before and after each treatment. The pre-treatment photo will serve as the baseline for comparison to follow-up photos to assess safety and efficacy. Skin instrumental measures may be taken with standard devices such as DSM II colorimeter (Cortex Technology, Hadsund, Denmark). Other instruments may measure skin properties or visualize the skin using an ultrasound device. Prior to each subsequent treatment, the investigator or his/her designee will review and update the medical condition and compliance with inclusion and exclusion criteria. The clinician will evaluate and grade the skin condition before each treatment and insure that the area has recovered suitably from the prior treatment(s) before proceeding to further treatments. In the event that treatment is delayed the investigator will record the specific skin condition and have subjects return after an additional 1 to 4 weeks for reassessment and subsequent treatments.

6.2 Anesthesia

Adjunctive cooling either by moist air, cool gel packs, or cool saline wipes may be used during and/or after treatment to enhance comfort. If subjects require additional means of reducing treatment or post-treatment discomfort, optional pre-treatment application of

topical anesthesia, such as BLT (20% benzocaine, 6% lidocaine, 4% tetracaine - Sobanko Derm Surg 2012), EMLA®, ElaMax® or Pliaglis® will be applied using an occlusive technique for up to 60 minutes prior to treatment. At the discretion of the Investigator, subjects may be given anesthesia with a local intradermal or nerve block injection of lidocaine with or without epinephrine, or equivalent, for areas treated at more aggressive settings. However, subjects will NOT be given sedation to the extent that all sensation is blunted and the subject is not able to verbally participate during the treatment process. If the pain becomes too uncomfortable, the treatment will be discontinued, or the settings on the laser can be lowered to a more comfortable level.

6.3 Analgesic and anxiolytic oral medications

At the discretion of the PI subjects may be offered oral analgesic and/or anxiolytic medication to further manage discomfort during treatment. Due to the side effects caused by these types of medications, subjects will be required to have a driver provide transportation for the procedure. These subjects must be willing to comply with pre-treatment medication instructions and sign the “Analgesic & Anxiolytic Medication Consent”.

6.4 Biopsies

In some subjects biopsies may be taken to evaluate the effect of treatment on the skin and to evaluate the safety and time course of healing. Biopsies are *optional* and may be taken immediately after treatment or at various days, weeks and monthly intervals post treatment. Biopsies will typically be of the punch type and range in diameter from 2- 6 mm, depending on the device setting and anatomic location. The areas of the skin to be biopsied will be numbed with an injection of local anesthetic. Biopsies will be retained for histological analysis. Subjects will return after an appropriate interval (5-7 days face, 10 – 14 days, trunk and limbs) depending on location of the biopsy on the body to have the sutures removed, or sutures may be removed during subsequent biopsy visit or another scheduled follow-up visit.

6.5 Study Treatment

Selection of settings will be based upon the practitioner's judgement and in accordance with treatment guidelines, publications and experience with similar ultrashort pulse laser devices. A series of test spots may be performed within the treatment area or on a less noticeable area with similar skin color and texture. After application of test spots, skin reactions will develop and can be evaluated for selection of setting parameters usually in 15 minutes for Skin Types I – III, but will take from 24 – 72hrs or longer to develop for darker skin types. For darker skin type subjects, if test spots are used to establish treatment settings, the treatment will take place on a separately scheduled session. To help evaluate performance the investigator may compare effects of the PicoPlus laser system to other FDA approved commercially available nanosecond or picosecond laser systems. Commercially available products will be used according to the manufacturer's recommendations and investigator's experience.

In preparation for treatment, the test spot or skin treatment area will be cleansed with mild soap and water and dried. If hair is present, the area should be shaved. Topical anesthetic cream such as BLT will be applied using an occlusive dressing technique for sufficient time (typically 45-60 min) to the point where adequate anesthesia is achieved. If topical anesthetic is used, the anesthetic will be thoroughly removed, the skin wiped clean and then sanitized with an antiseptic scrub such as Hibiclens®. If discomfort is experienced during treatment, subjects may be offered adjunctive cooling such as cold air, cool gel packs, or cold moist cloths. Subject discomfort during study treatment will be documented using a 0 (None) to 10 (Severe) pain rating scale. Mild discomfort is typical during the treatment of benign pigmented lesions. For tattoo removal treatments, because settings are typically higher, moderate to significant discomfort is frequently reported. Most patients describe the discomfort as less than when the tattoo was applied. Some areas are more sensitive than others. Subjects may request that treatment be discontinued at any time for any reason.

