10.1 Potential Risks

There is a risk of adverse events, skin reactions or side effects. Expected side effects include:

- Discomfort. Mild discomfort is typical during the treatment of benign pigmented lesions. For tattoo removal treatments, where higher settings are typically used, moderate to significant discomfort is frequently reported. Most patients describe the discomfort as less than when the tattoo was applied. Some areas are more sensitive than others.
- Edema and erythema. Swelling and redness often occur, but will subside in 2-5 days and can be reduced with regular ice application.
- Purpura. The area may appear to be bruised after treatment. The bruising will typically fade in 5-7 days.
- Texture changes. Transient texture changes are often noted, but usually resolve with time. Blisters/scabs/crusting. These may occur and usually take 4-10 days to heal and up to 2 weeks for off-face treatments.
- Petechia or pinpoint bleeding. For tattoo removal treatments, pinpoint bleeding or

- oozing may develop and can continue up to 2 days post-treatment. Pinpoint bleeding is less common during treatment of benign pigmented lesions but may develop and will typically resolve within a few hours post-treatment.
- Hyper/hypopigmentation. Skin can develop temporary lightening or darkening after laser treatment. Hyperpigmentation can be worsened with sun exposure. Hypopigmentation usually occurs after multiple treatments. Pigmentary issues typically resolve with time, but can be permanent.
 - Allergic reaction. Patients who have had a prior allergic reaction to ink during tattoo application may have a similar reaction after laser treatment. This reaction can be controlled by a pre-treatment and/or post-treatment regimen of steroids and antihistamines.
 - Infection. Despite good wound care, pain, swelling, oozing, and fever can indicate the development of an infection. Topical and/or oral antibiotics may be necessary.
 - Scarring. Scarring is a rare occurrence, but it is a possibility if the skin's surface is disrupted. To minimize the chances of scarring, it is important that patients follow all post-treatment instructions provided by their healthcare provider. Good post-treatment care can help reduce the possibility of scarring.
 - Darkening of lesions. Lesions will darken post-treatment and will slough 5-21 days post-treatment.

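### When test spots are placed inside the treatment area, the photo schedule allows a baseline photograph of skin that has already been lasered

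*Protocol*

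**What the plan says.** Test spots are optional, and the treatment area itself is one of the permitted places for them. Protocol section 6.5: "A series of test spots may be performed within the treatment area or on a less noticeable area with similar skin color and texture". Their reactions can be read "usually in 15 minutes for Skin Types I – III", "but will take from 24 – 72hrs or longer to develop for darker skin types". For the darker types the section continues: "if test spots are used to establish treatment settings, the treatment will take place on a separately scheduled session".

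Photographs are tied to treatments. Section 6.1: "High-resolution digital photographs will be taken before and after each treatment". It then fixes the baseline: "The pre-treatment photo will serve as the baseline for comparison to follow-up photos to assess safety and efficacy".

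In Table 3 (section 5.2.2), the row "Pre-Tx Clinical Photos" is empty in the screening column and first marked at the first treatment visit. The table has no column for a test-spot session. Section 9.1 calls for photographs and grading at baseline but does not place baseline before or after test spots.

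**The concern.** The trial has a single open-label arm in which each subject is compared with his or her own earlier condition (section 5.2). No concurrent control absorbs a distorted starting point, so the baseline record carries much of the inference.

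If test spots are placed in the area to be graded at one session, and the first photograph is taken at the next, the before picture shows lasered skin. Spots that are darkened, crusted or bruised at that moment would make later clearing look larger. Spots that have already lightened would make it look smaller. A photograph that was never taken cannot be recovered at analysis, so this belongs to the protocol's procedures and not to an analysis plan.

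**Working it through.** The protocol gives no figure to reproduce. The check sets the passages side by side and then illustrates the size under stated assumptions.

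**1. Can laser exposure precede the first scheduled photograph?**

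| Step | Source | Content |
|---|---|---|
| Spots may lie in the treatment area | 6.5 | Optional; elsewhere is also allowed |
| Spots may come at an earlier session | 6.5 | Prescribed for darker skin types if spots are used to choose settings |
| Darker types are eligible | 4.1 | Group A types I–VI, Group B types I–IV |
| Photographs before and after each treatment | 6.1 | Test-spot sessions not mentioned |
| First photo mark | Table 3 | First treatment visit; screening cell empty |
| Spots left out of grading | none | The investigator scale (Appendix B, 18.1) grades the treated area |

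Section 6.5 separates test spots from the treatment that follows them. Read literally, the schedule therefore allows the sequence test spots, then first photograph, then treatment. For types I–III the spots can be read within the same visit. There the order of photograph and test spots is simply not stated.

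**2. Could a reaction be visible at that photograph?** Section 10.1 says of treated lesions: "Lesions will darken post-treatment and will slough 5-21 days post-treatment". It also gives 5–7 days for bruising and 4–10 days for blisters and crusts, up to 2 weeks off the face. These figures describe treatments, not test spots, and the protocol sets no interval between test spots and the first treatment. They show only that laser effects can be visible for days to weeks.

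**3. Which outcomes use the photograph?**
- Directly: the blinded review of photo pairs (18.4, optional) and the MASI grading of baseline and later photos (18.5).
- Possibly: the subject's rating of improvement against baseline (18.2), since Appendix A offers the photos as an aid, and the investigator's rating (18.1), which does not say what it is compared with.
- Not necessarily: satisfaction (18.3).
- A colorimeter reading is not a photograph, but it has the same weakness if first taken after test spots.

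**4. Illustration of size.** The inputs t and k are assumptions; the protocol gives neither.
- t = share of the graded area covered by spots, 5% or 10%
- k = change in pigment within the spots, 50%
- c = true clearing
- B = pigment in the baseline photo relative to untreated skin: 1 − tk if the spots have lightened, 1 + tk if they have darkened
- Apparent clearing = 1 − (1 − c)/B

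| c | t | Spots | B | Apparent clearing |
|---|---|---|---|---|
| 50% | 5% | lightened | 0.975 | 1 − 0.50/0.975 = 48.7% |
| 50% | 10% | lightened | 0.950 | 1 − 0.50/0.950 = 47.4% |
| 50% | 5% | darkened | 1.025 | 1 − 0.50/1.025 = 51.2% |
| 50% | 10% | darkened | 1.050 | 1 − 0.50/1.050 = 52.4% |
| 48% | 10% | darkened | 1.050 | 1 − 0.52/1.050 = 50.5% |

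The shifts are 1.2 to 2.6 points. In the first two rows grade 2 becomes grade 1; in the last, grade 1 becomes grade 2. In the third and fourth the grade does not change.

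The shift equals (1 − c)(1 − 1/B), so it is larger at low clearing:
- At the 25% cut-off with t = 10%: 0.75 × (1 − 1/0.95) = −3.9 points, or 0.75 × (1 − 1/1.05) = +3.6.
- At the 75% cut-off with t = 5%: 0.25 × (1 − 1/0.975) = −0.6 points, or 0.25 × (1 − 1/1.025) = +0.6.

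**The case against.** The strongest reply is that the protocol permits this sequence but does not compel it. Test spots are optional and may lie outside the area, and the separate session is prescribed only for darker skin. Section 9.1 asks for photographs at baseline. Section 6.5 gives the same skin preparation for a test spot as for the treatment area, so a site could regard a test-spot session as laser treatment and photograph first. Table 3 omits test-spot sessions altogether; it does not tell staff to skip a photograph there. All of this stands. It limits how many subjects are affected, but it does not close the gap, because nowhere is a photograph required before the first laser pulse.

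Some stronger readings are tempting but unsupported:
- A reader might infer that every efficacy measure is corrupted. Satisfaction ratings involve no baseline photograph, and the investigator's rating is not stated to be made from photographs.
- A reader might infer that comparisons across Fitzpatrick types are distorted. The protocol plans no such comparison, and Group B stops at type IV, so types V and VI enter only for tattoos.
- A reader might infer a large bias from spots filling a small lesion. The protocol gives neither the number nor the size of test spots, so no such figure can be derived.

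It is also fair to say that this is an exploratory pilot and that the direction of any error is unknown.

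**Conclusion.** The point holds in a conditional form. Where test spots are placed within the treatment area, and above all where darker skin leads to a separate treatment session, the written schedule allows a baseline photograph that already shows laser effect. The blinded review and the MASI grading are exposed; investigator and subject improvement ratings can be influenced.

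The protocol does not show that this will happen in every such subject, nor how large the error is or which way it goes. With 5–10% of the area altered by 50%, the shift is about 1 to 3 percentage points around 50% clearing, and 0.6 to 3.9 points across the three grade cut-offs. That changes a grade only for subjects close to a cut-off. The effect is probably modest, but it is worth correcting because it cannot be repaired later and the remedy is cheap.

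**What to change.** In section 6.1 and Table 3, define baseline as the standardized photograph, together with the baseline grading or colorimeter reading where used, obtained before the first laser exposure of any kind, test spots included. In Table 3, add a photo mark at the screening or test-spot session. Where test spots and treatment fall in one visit, the same definition settles the order.

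The cost is one extra photo set for subjects who have a separate test-spot session. It needs no additional staff and changes no device setting or clinical rule.
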